#### **1.4.4 Visits windows**

*Visit-windows* will be used for the data that is summarized by analysis visit; they are based on the study evaluation schedule and comprise a set of days around the nominal visit day. For any assessment, there are the protocol defined scheduled visits around which visit windows were created to cover the complete range of days within the study. The visit windows are shown in [Table 1-8](#)

. In this table, the days are counted since the first dose of study treatment (study days) for safety assessments, and the days are counted since the date of randomization for efficacy assessments. These visit windows apply to measurements taken at every visit. For assessments collected less often different visit windows will be applied as detailed below.

When visit windows are used, all visits will be re-aligned, i.e., they will be mapped into one of the visit windows. E.g., if the *Week 4* visit of a subject is delayed and occurs on Day 46 instead of on Day 29, say, it will be re-aligned to visit window *Week 8*. In the case of major deviations from the visit schedule, or due to unscheduled visits, several assessments of a subject may fall in a particular visit window (either scheduled or unscheduled). Statistical approaches to handle multiple assessments in a given visit window are specified below.

Of note, subjects are allowed to have gaps in visits.

**Table 1-8      Assessment windows for scheduled visits**

| Analysis Visit             | Week
(relative to
baseline of
core) | Scheduled Day | Visit Window       |
|----------------------------|--|---------------|--------------------|
| Baseline                   | BSL  | 1             | -28 days to Day 1* |
| Week 1                     | 1  | 8             | Day 2-11           |
| Week 2                     | 2  | 15            | Day 12-18          |
| Week 3                     | 3  | 22            | Day 19-25          |
| Week 4                     | 4  | 29            | Day 26-43          |
| Week 8                     | 8  | 57            | Day 44-71          |
| Week 12                    | 12   | 85            | Day 72-99          |
| Week 16                    | 16   | 113           | Day 100-127        |
| Week 20                    | 20   | 141           | Day 128-155        |
| Week 24                    | 24   | 169           | Day 156-183        |
| Week 28                    | 28   | 197           | Day 184-211        |
| Week 32                    | 32   | 225           | Day 212-239        |
| Week 36                    | 36   | 253           | Day 240-267        |
| Week 40                    | 40   | 281           | Day 268-295        |
| Week 44                    | 44   | 309           | Day 296-323        |
| Week 48                    | 48   | 337           | Day 324-351        |
| Ext1 Week 52 / Screening 2 | 52   | 365           | Day 352-379        |
| Week 56                    | 56   | 393           | Day 380-407        |
| Week 60                    | 60   | 421           | Day 408-435        |
| Week 64                    | 64   | 449           | Day 436-463        |
| Week 68                    | 68   | 477           | Day 464-491        |
| Week 72                    | 72   | 505           | Day 492-519        |
| Week 76                    | 76   | 533           | Day 520-547        |
| Week 80                    | 80   | 561           | Day 548-575        |
| Week 84                    | 84   | 589           | Day 576-603        |
| Week 88                    | 88   | 617           | Day 604-631        |
| Week 92                    | 92   | 645           | Day 632-659        |
| Week 96                    | 96   | 673           | Day 660-687        |
| Week 100                   | 100  | 701           | Day 688-715        |
| Week 104                   | 104  | 729           | Day 716-743        |
| Week 108                   | 108  | 757           | Day 744-771        |
| Week 112                   | 112  | 785           | Day 772-799        |

|          |     |      |               |
|----------|-----|------|---------------|
| Week 116 | 116 | 813  | Day 800-827   |
| Week 120 | 120 | 841  | Day 828-855   |
| Week 124 | 124 | 869  | Day 856-883   |
| Week 128 | 128 | 897  | Day 884-911   |
| Week 132 | 132 | 925  | Day 912-939   |
| Week 136 | 136 | 953  | Day 940-967   |
| Week 140 | 140 | 981  | Day 968-995   |
| Week 144 | 144 | 1009 | Day 996-1023  |
| Week 148 | 148 | 1037 | Day 1024-1051 |
| Week 152 | 152 | 1065 | Day 1052-1079 |
| Week 156 | 156 | 1093 | Day 1080-1107 |

For AIN457 300mg FI/AIN457 300mg SoR switch to AIN457 300mg FI/AIN457 150mg FI/AIN457 150mg FI switch to AIN457 300mg FI/AIN457 150mg SoR switch to AIN457 300mg FI

|          |     |      |                 |
|----------|-----|------|-----------------|
| Week 168 | 168 | 1177 | Day 1108-1219   |
| Week 180 | 180 | 1261 | Day 1220-1303   |
| Week 192 | 192 | 1345 | Day 1304-1401   |
| Week 208 | 208 | 1457 | Day 1402-1499   |
| Week 220 | 220 | 1541 | Day 1500-1583   |
| Week 232 | 232 | 1625 | Day 1584-1667   |
| Week 244 | 244 | 1709 | Day 1668-1765   |
| Week 260 | 260 | 1821 | Day 1766-1835   |
| Week 264 | 264 | 1849 | Day 1836 – 1863 |
| Week 268 | 268 | 1877 | Day 1864 - 1891 |

For AIN457 300mg SoR/AIN457 150mg SoR

|          |     |      |               |
|----------|-----|------|---------------|
| Week 160 | 160 | 1121 | Day 1108-1135 |
| Week 164 | 164 | 1149 | Day 1136-1163 |
| Week 168 | 168 | 1177 | Day 1164-1191 |
| Week 172 | 172 | 1205 | Day 1192-1219 |
| Week 176 | 176 | 1233 | Day 1220-1247 |
| Week 180 | 180 | 1261 | Day 1248-1275 |
| Week 184 | 184 | 1289 | Day 1276-1303 |
| Week 188 | 188 | 1317 | Day 1304-1331 |
| Week 192 | 192 | 1345 | Day 1332-1359 |
| Week 196 | 196 | 1373 | Day 1360-1387 |
| Week 200 | 200 | 1401 | Day 1388-1415 |
| Week 204 | 204 | 1429 | Day 1416-1443 |
| Week 208 | 208 | 1457 | Day 1444-1471 |
| Week 212 | 212 | 1485 | Day 1472-1499 |

|          |     |      |                 |
|----------|-----|------|-----------------|
| Week 216 | 216 | 1513 | Day 1500-1527   |
| Week 220 | 220 | 1541 | Day 1528-1555   |
| Week 224 | 224 | 1569 | Day 1556-1583   |
| Week 228 | 228 | 1597 | Day 1584-1611   |
| Week 232 | 232 | 1625 | Day 1612-1639   |
| Week 236 | 236 | 1653 | Day 1640-1667   |
| Week 240 | 240 | 1681 | Day 1668-1695   |
| Week 244 | 244 | 1709 | Day 1696-1723   |
| Week 248 | 248 | 1737 | Day 1724-1751   |
| Week 252 | 252 | 1765 | Day 1752-1779   |
| Week 256 | 256 | 1793 | Day 1780-1807   |
| Week 260 | 260 | 1821 | Day 1808-1835   |
| Week 264 | 264 | 1849 | Day 1836 – 1863 |
| Week 268 | 268 | 1877 | Day 1864 - 1891 |

\* Baseline measurement before the first drug administration for safety assessments and before the first randomization in CAIN457A2304 for efficacy assessments. The days are counted since the first dose of study treatment for safety assessments, and the days are counted since the date of randomization for efficacy assessments.

For parameters which are not collected at every visit (e.g. weight, DLQI, EQ-5D, HAQ-DI), visit windows defined in the tables above will be combined. E.g., if a parameter is measured at Week 12 and Week 24 only, Week 12 visit window will extend from Day 2 to Day 99 (combining Week 1 to Week 12 visit windows), Week 24 will extend from Day 100 to Day 183 (combining Week 13 to Week 24). If more than one assessment falls into the interval, the rules defined in [Section 1.4.5](#) below are applied.

Maintenance period visits will not be mapped into induction period, and induction period visits will not be mapped into maintenance period. For example, if a subject is coming late for the Week 12 visit (induction period), and the visit would fall into the Week 13 (maintenance period) visit window, it would not be mapped for the analysis.

#### 1.4.5    Multiple assessments within visit windows

When there are *multiple assessments* in a particular visit window, the following rules are applied to select one value “representing” the subject in summary statistics in a visit window (See [Table 1-8](#) & [Table 1-9](#)).

For baseline assessment definition see [Section 1.4.3](#). For post-baseline visit windows the following applies (unless otherwise specified):

- for *quantitative variables*, the *closest* to the actual visit is chosen (if two assessments have the same distance, then the earlier one will be chosen);
- for *qualitative variables*, the *worst* record is selected. It is noted that in the analyses performed, *worst* case is always well defined (e.g., for urine protein values “+” and “++”, the *worst* case is defined as “++”),

- in case qualitative variables are based on quantitative variables, e.g. PASI 75 response, the visit will be assigned to the quantitative variable, and this visit will be used for the derived qualitative variable.

**Table 1-9      Rules for selecting values for analysis**

| Timing of measurement  | Type of data   | Rule   |
|------------------------|--|--|
| Baseline               | All data   | See Section 1.4.3  |
| Post-baseline efficacy | All data except DLQI, EQ-5D and health assessment            | The measurement closest to the target day will be used. In the event two measurements are taken equally apart (e.g., 1 day before target date and 1 day after), the earlier one will be used.  |
| Post-baseline efficacy | DLQI, EQ-5D and health assessment                            | The measurement closest to the target day will be used. In the event two measurements are taken equally apart the earlier one will be used.
If two measurements have been taken on the same day, select the worst.  |
| Post-baseline safety   | Summary visit information (e.g. lab, ECG, etc.)              | The measurement closest to the target day will be used. In the event two measurements are taken equally apart (e.g., 1 day before target date and 1 day after), the earlier one will be used.
If two measurements are taken on the same date/different time then select the first one(using the time);
If two measurements are taken on the same date/time/different visit number then use the first visit number (assuming this is the planned visit);
If two measurements are taken on the same date/time/CRF visit then take the average value |
| Post-baseline safety   | Notable abnormalities (e.g., vital signs, ECG), CTCAE grades | The most extreme measurement in the window will be used. Note this means a subject can have a notably high and notably low measurement within a window (analysis period).  |

#### **1.4.6      Day of last dose of study treatment**

The date of last dose will be collected via the CRF. The subject's exposure will be calculated considering the end of treatment period visit including follow-up 1 period or the last dose date +84 days which happened earlier.

## **1.5 Subject disposition, background and demographic characteristics**

### **1.5.1 Subject disposition**

The number and percentage of subjects in the randomized set who entered and completed study periods), and who discontinued the study prematurely (including the reason for discontinuation) will be presented for each treatment group. The reason for patients discontinuation from study treatment will be presented by yearly interval (analysis visit) for AIN457 150 mg (switch+non-switch) and AIN457 300 mg.

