The results of protocol CAIN457A2304 showed that the re-treatment at start of relapse maintenance regimen (SoR) was not non-inferior to a fixed interval regimen (FI) with treatment every four weeks and that patients experienced better maintenance of effect with secukinumab 300 mg compared to secukinumab 150 mg; therefore, this amendment introduces an opportunity at week 156 for blinded subjects to 1) switch off of the SoR treatment regimen to treatment every four weeks and 2) to increase the secukinumab dose to 300 mg. All subjects will be unblinded at Week 156 and the investigator may switch to the subject one of these open label treatment option(s) depending on the current treatment assignment:

Previous treatment arm through Week 152 (Unblinded at Week 156)	Treatment options, as decided by the investigator	Office visit frequency after Week 156
Secukinumab 300 mg FI	Continue secukinumab 300 mg FI	Every 12-16 weeks
Secukinumab 300 mg SoR	Continue secukinumab 300 mg SoR for remainder of the study OR Switch to secukinumab 300 mg dosed every 4 weeks	Every 4 weeks Every 12-16 weeks
Secukinumab 150 mg FI	Continue secukinumab 150 mg FI OR Switch to secukinumab 300 mg dosed every 4 weeks	Every 12-16 weeks Every 12-16 weeks
Secukinumab 150 mg SoR	Continue secukinumab 150 mg SoR for remainder of the study OR Switch to secukinumab 300 mg dosed every 4 weeks	Every 4 weeks Every 12-16 weeks

Additionally, this amendment extends the treatment duration for an additional 104 weeks (for a total of 5 years, one year in the core study or studies and four years in the extension study) and the opportunity for home administration of the study drug. In case secukinumab becomes commercially available in a participating country, the study might be discontinued in the respective country. This extension of treatment will allow for safety, tolerability, and efficacy data to be collected from the participating subjects for up to a total of 5 years.

At the time of this amendment, recruitment is complete with 675 subjects randomized into the trial across 15 countries and 112 sites and approximately 108 subjects have discontinued from the study. Since recruitment is complete and there is no change to protocol-mandated discontinuation, it is not expected that this amendment will have an impact on the study population or have a significant impact on the primary objective of the trial.

Changes to the protocol

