**Retreatment at start of relapse regimen – “SOR”: “start of relapse” either 150 or 300 mg s.c. secukinumab:** “Start of relapse” will be defined as a loss of  $\geq 20\%$  of the maximum PASI gain achieved during the study compared to baseline, *and* a loss of PASI 75 response. Whenever a subject fulfills the start of relapse criteria, active secukinumab will be administered at their scheduled visits (i.e. every four weeks) until the subject is back to PASI 75 response. The dose administered in the maintenance period (secukinumab 150 mg or 300 mg) will be identical to the dose that these subjects received during the induction period. If a subject does not fulfill the criteria of a start of relapse or is back to PASI 75 response after a start of relapse, they will receive placebo injections (two injections per dose) to maintain the blind. This treatment regimen is applied every four weeks, from week 12 up to and including week 48.

**Open label (OL) 300 mg s.c. secukinumab:** All the partial responders at week 12 in induction period in A2304 will enter A2307 double blind i.v. period (for 8 weeks) and these subjects will be randomized with 1:1 ratio into either “300 mg s.c. secukinumab” or “10 mg per kg i.v. secukinumab”. All the subjects will enter open label 300 mg s.c. secukinumab maintenance period from week 8 to week 40.

All the subjects who are eligible from the above 5 treatment groups (4 treatment groups from A2304 and 1 treatment group from A2307) enter the A2304E1 extension study treatment period and continue with same treatment groups. At Week 156, patients under AIN457 150mg FI arm, AIN457 150mg SOR arm, and AIN457 300mg SOR arm could be switched to AIN457 300mg FI arm as determined by physician’s judgement.

For the final analysis, data will be presented for the following treatment groups:

- AIN457 150 mg FI
- AIN457 150 mg FI switch to AIN457 300mg FI
- AIN457 150 mg FI combined non-switch and switch
- AIN457 300 mg FI
- AIN457 150 mg SoR non-switched
- AIN457 150mg SoR switch to AIN457 300mg FI
- AIN457 300 mg SoR non-switched
- AIN457 300mg SoR switch to AIN457 300mg FI
- AIN457 300 mg OL
- Any AIN457 300mg
- Any AIN457 150mg
- Any AIN457

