**Table 1-2 Analysis by treatment group**

| Endpoint/analysis  | AIN457 150 mg FI
AIN457 150 mg FI switch to 300mg FI
AIN457 300 mg FI
AIN457 150 mg SoR
AIN457 150 mg SoR switch 300 mg FI
AIN457 300 mg SoR
AIN457 300 mg SoR switch 300 mg FI
AIN457 300mg OL | AIN457 150mg FI(NSW+SW) | Any AIN457 150mg
Any AIN457 300mg | Any AIN457 |
|--|--|-------------------------|--------------------------------------|------------|
| Subject disposition  | X  |                         |                                      | X          |
| Demography & baseline characteristics                        | X  |                         |                                      | X          |
| Previous & concomitant medication                            | X  |                         |                                      | X          |
| Medical history  | X  |                         |                                      | X          |
| Study medication: duration of exposure                       | X  |                         | X                                    | X          |
| Maintanance of PASI 75 response                              | X  |                         |                                      |            |
| PASI 50/75/90/100 and IGA mod 2011 0 or 1 response over time | X  | X                       |                                      |            |
| PASI score over time   | X  | X                       |                                      |            |
| IGA mod 2011 score over time                                 | X  | X                       |                                      |            |
| Relapse  | X  |                         |                                      |            |
| Rebound  | X  |                         |                                      |            |
| DLQI 0 or 1 achievement                                      | X  | X                       |                                      |            |

|                          |  |                         |                                      |            |
|--------------------------|--|-------------------------|--------------------------------------|------------|

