### **1.5.2 Background and demographic characteristics**

The following common background and demographic variables from **core** study will be analyzed for assessing the baseline comparability:

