### **1.8.3 Testing strategy**

No formal hypothesis testing will be performed for this extension study.

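### The main disposition and baseline tables are split by the Week 156 switch with no assigned-arm totals for 150 mg FI and the two SoR arms, so their discontinuation percentages are not directly comparable with 300 mg FI

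*SAP*

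**What the plan says.** SAP 1.2 introduces its group list with "For the final analysis, data will be presented for the following treatment groups". The list separates switched from non-switched subjects in 150 mg FI, 150 mg SoR and 300 mg SoR; one entry, for example, is "AIN457 150 mg SoR non-switched". It has a combined switch and non-switch group for 150 mg FI only.

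In SAP Table 1-2, the rows for "Subject disposition" and for demography and baseline characteristics carry marks in two places: the eight split groups and Any AIN457. The combined 150 mg FI column is blank in both rows, and there is no combined SoR column.

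SAP 1.5.1 tabulates entry, completion and discontinuation in the randomized set. Those "who discontinued the study prematurely (including the reason for discontinuation) will be presented for each treatment group". It then adds reasons for stopping study treatment, "presented by yearly interval (analysis visit) for AIN457 150 mg (switch+non-switch) and AIN457 300 mg".

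SAP 1.5.2 lists baseline variables that "will be analyzed for assessing the baseline comparability", by treatment group and in total, on the FAS. The SAP 1.2 definition of the FAS lets the Week 156 reassignment change a subject's group. Protocol 9.1 keeps the group from core-study randomization.

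Under Protocol Table 5-1 and SAP 1.2, switching is possible only at Week 156, at the investigator's discretion. It is open to 150 mg FI, 150 mg SoR and 300 mg SoR, but not to 300 mg FI.

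**The concern.** Membership of a switched column requires staying until Week 156. The switched columns therefore contain no early leavers, and the non-switched columns contain all of them, over a denominator from which the switchers have been removed. 300 mg FI is untouched by this. Even if the assigned arms behaved identically, the main disposition table would show more early discontinuation in the three non-switched columns than in 300 mg FI. Tolerability is part of the primary objective, so a reader may well use this table to compare regimens.

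The baseline table has a related weakness. Its columns for three of the four arms from core study A2304 are formed by a decision taken two years after extension entry. Differences between those columns partly describe who was switched. The secondary objective compares SoR with FI at Weeks 92 to 156 on assigned treatment, yet the plan marks no assigned-arm baseline column for the three split arms.

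**Working it through.** **Inputs**
- Planned arm size: 148 per A2304 arm (Protocol 9.7). Check: 918 × 0.95 × 0.85 = 741.3, stated as 740; 741.3 × 0.80 / 4 = 148.3, stated as 148.
- Early discontinuation: the Amendment 1 rationale reports that "approximately 108 subjects have discontinued from the study", out of 675. 108 / 675 = 16.0%. This is approximate, pooled over all groups including open-label, and taken at a calendar date. That amendment introduced the switch, so none of these subjects could have switched.
- Share switching at Week 156: not in the documents. It is assumed and varied.
- The documents state no discontinuation figure by column, so there is none to reproduce.

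**Leaving before Week 156**

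Let d be the share leaving early, equal in every arm, and s the share of the remainder who switch. The non-switched column holds 1 − (1 − d)s of the arm, so the early-leaver percentage shown there is d / [1 − (1 − d)s].

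With d = 0.16:

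| s | Non-switched column | Switched column | 300 mg FI |
|---|---|---|---|
| 30% | 0.16 / 0.748 = 21.4% | 0% | 16% |
| 50% | 0.16 / 0.580 = 27.6% | 0% | 16% |
| 70% | 0.16 / 0.412 = 38.8% | 0% | 16% |

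**The same in whole subjects, 148 per arm**

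24 leave early and 124 remain. With 25%, 50% or 75% switching (31, 62 or 93 subjects), the non-switched column shows 24/117 = 20.5%, 24/86 = 27.9% or 24/55 = 43.6%. The whole arm is 24/148 = 16.2%.

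**Total discontinuation, adding later leavers**

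The planned table counts all discontinuations, so later leavers matter. Suppose 10% of those remaining leave after Week 156, in switched and non-switched columns alike:
- Whole arm: (24 + 12.4) / 148 = 24.6%.
- Non-switched, 25% switching: (24 + 9.3) / 117 = 28.5%.
- Non-switched, 50% switching: (24 + 6.2) / 86 = 35.1%.
- Non-switched, 75% switching: (24 + 3.1) / 55 = 49.3%.
- Switched: 10%.

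**What a combined column does**

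Adding the two columns of an arm returns the whole-arm rate exactly. In the 50% case above, (30.2 + 6.2) / 148 = 24.6%.

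**What can be recovered from the planned tables**

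The switched and non-switched columns partition each arm. Counts add, and the pooled mean is (n₁m₁ + n₂m₂) / (n₁ + n₂). SDs can be pooled from N, mean and SD, all of which SAP 1.1 requires. Medians and quartiles, which SAP 1.1 also lists, cannot be recovered.

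**The case against.** **The combined view is already planned for 150 mg.** The yearly display in SAP 1.5.1 removes the artefact for that dose and isolates the years before Week 156. This stands in part. The display gives reasons for stopping treatment, not the main table's entered, completed and discontinued percentages. It does not say whether SoR is included; the comparable yearly outputs in SAP 1.6 and 1.9.1 are limited to FI. It does nothing for the baseline table.

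**For 150 mg FI the SAP may simply be inconsistent.** SAP 1.2 lists the combined group and 1.5.1 promises each treatment group, while Table 1-2 leaves the cell blank. That is fair: for this arm the text and the table need reconciling. For SoR no combined group is listed at all.

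**Arm comparability is not lost.** A reader might infer that assigned arms cannot be compared. The documents do not support that, because counts and means can be pooled by hand.

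**Tolerability does not rest on this table.** A reader might infer that the plan will show 150 mg FI and SoR as much worse tolerated than 300 mg FI. Protocol 9.4 places the primary analysis in 9.5.2. SAP 1.9.1 plans separate summaries of adverse events leading to discontinuation, and yearly crude and exposure-adjusted rates for the FI cohorts, with exposure censored at the switch date. So that inference is too strong. The yearly analyses, however, cover FI only and are not disposition or baseline displays.

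**The split columns have a use, and nothing is tested.** Efficacy and safety are reported in those columns, so baseline data there help interpret them. Assigned-arm totals would not be intact randomized arms either, since entry required completing the core study and expected benefit. The SAP also states: "No formal hypothesis testing will be performed for this extension study". All of this is correct. It argues for keeping the split columns as description, not for omitting the totals.

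**Conclusion.** The point holds as a matter of table layout. As marked in Table 1-2, discontinuation percentages for 150 mg FI, 150 mg SoR and 300 mg SoR are not directly comparable with those for 300 mg FI. No assigned-arm baseline column is marked for those three arms. The gap is clearest for SoR. For 150 mg it is partly covered by the yearly display, and elsewhere it can be partly undone by pooling columns.

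The direction of the early-leaver effect is structural; its size is hypothetical. The figures of 21%, 28% and 39% against 16% assume the same 16% in every arm and switch shares of 30%, 50% and 70%, which the documents do not give. The 16% should not be read as a floor for each arm, because it is pooled over all groups. Nor should 0% be expected in the switched columns of the planned table, which also counts later leavers. For total discontinuation, in the 50% case with no later leavers among non-switchers, the gap would close if about 28% of switchers later discontinued. The imbalance before Week 156 would remain.

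**What to change.** In SAP Table 1-2, mark the disposition and demography rows for the existing combined 150 mg FI column, and add combined 150 mg SoR and combined 300 mg SoR columns for those two rows. State in 1.5.1 and 1.5.2 that discontinuation and baseline comparability between assigned arms are read from these columns beside 300 mg FI. Show disposition by switch status only among subjects who reached Week 156, as description. In 1.5.1, also state whether the yearly 150 mg and 300 mg display is FI only.

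The cost is two more columns, a few words in the SAP and a little programming. No new data are needed.
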